2. SCHEDULE OF ACTIVITIES (SOA)

Procedure	Study Period					Notes
	Screening ¹	Day 1	Day 2	Day 3	Up to day 28	
Start of mechanical ventilation	X					
Inclusion/exclusion criteria	X					Reason for intubation (underlying diagnosis e.g. sepsis, pneumonia) to be collected where possible.
Informed consent (ICF)	X					Consent process will be followed as outlined in Informed Consent Process (Section 12.3.3)
Demography	X					If it is not possible to collect at screening can be collected at any point during the study.
Height and weight	X					Collected for the purposes of evaluating BMI. Clinical estimates are acceptable if direct measurement is not possible.
Medical history	X					If possible to collect, includes medication and cardiovascular risk factors. If it is not possible to collect at screening can be collected at any point during the study.
Diagnosis of pulmonary circulatory dysfunction (PCD) and acute cor pulmonale (ACP)		X	X	X		As per echocardiographic output.
Participant status	X	X	X	X		Intubation status, prone status; diagnosis of acute respiratory distress syndrome (ARDS) including severity at time of diagnosis (if available). Post screening status to be assessed at the same time point as echocardiogram (\pm 1 hour).
Participant management	X	X	X	X		Management with extracorporeal membrane oxygenation (ECMO) and extracorporeal CO ₂ (ECCO ₂ R) removal. Post screening status to be assessed at the same time point as echocardiogram (\pm 1 hour).
Simplified acute physiology score (SAPS II)	X					To be taken within approximately 24 hours of admission into the intensive care unit, as per standard of care.

Procedure	Study Period					Notes
	Screening ¹	Day 1	Day 2	Day 3	Up to day 28	
Sequential Organ Failure (SOFA) score	X	X	X	X		
Echocardiogram		X	X	X		Transthoracic echocardiogram (TTE) and/or transoesophageal echocardiogram (TOE). First echocardiogram must be completed within 48 hours of starting mechanical ventilation (but \leq 24 hours, whenever possible); the following echocardiograms will be undertaken as per standard of care 24 hours apart (\pm 2 hours) on subsequent consecutive days (Day 2 and 3).
Vital signs	X ³	X	X	X		Blood pressure (mean arterial, systolic and diastolic), heart rate, body temperature to match echocardiogram time points (\pm 30 minutes) ² .
Laboratory assessments	X	X	X	X		Clinical chemistry and haematology.

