4. ANALYSIS POPULATIONS

Population ¹	Definition / Criteria	Analyses Evaluated
Screened	All participants who have been screened.	
• To aid construction of Consort diagram in any publication
Enrolled	All participants who had passed screening and who had appropriate informed consent (via any of the processes described in the protocol).	
• Summary of Subject Status and Reason for Study Withdrawal• Summary of Study Populations• Summary of Exclusions from the

Population ¹	Definition / Criteria	Analyses Evaluated
		Safety/Completed/ Evaluable Populations
Safety	All participants for whom at least one echocardiograph and/or blood sample has been taken, and who did not retrospectively withdraw the consent.	
 • Study population (excl. specific tables mentioned below) • Safety
Evaluable	All participants for whom PASP, RV size ratio, Ang II and Ang(1-7) data have been recorded for at least one study time point, and who did not retrospectively withdraw the consent (and who still had at least one study time point of data remaining after accounting for any prohibited concomitant medications (for example but not limited to renin inhibitors, ARBs or ACE inhibitors) – See Section 10.1.1).	
 • Pharmacodynamic/ Biomarker (excl. disease diagnosis status)
Evaluable with Prohibited Con Meds	All participants in the Evaluable population plus any participants who were excluded from the Evaluable population because of prohibited concomitant medications (for example but not limited to renin inhibitors, ARBs or ACE inhibitors)	
 • Sensitivity for Primary analysis (conditional on number of prohibited con meds)
Completed ²	All participants for whom PASP, RV size ratio, Ang II, and Ang(1-7) data have been recorded for all three study days.	
 • Disease diagnosis status
At Risk	
For the purpose of evaluating ACP/PCD and ARDS incidence rates the participants who satisfy
 
1) PASP and RV size ratio recorded for all three study days (regardless of the Ang II and Ang(1-7) status)
 
and/or
 
2) databased ACP/PCD and/or ARDS assessment during the study period (even if they do not have three days' worth of study assessments for the above echo outcomes)
 
provided consent is not withdrawn.
	
 • Disease diagnosis status

NOTES :

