7.2. Secondary Efficacy Analyses

7.2.1. Endpoint / Variables

The variables to be included in the secondary pharmacodynamic analysis are the same as for the primary pharmacodynamic analysis, with the addition of the following independent variables:

- Ang(1-7) on Study Days 1, 2 and 3
- (Optionally) Ang(1-5) on Study Days 1, 2 and 3 (if the correlation between Ang(1-7) and Ang(1-5) values is not too high – otherwise the analysis would not be expected to add additional insights/value)
- Note: The planned modelling using similar techniques to the primary analysis for the Ang II/Ang(1-7) response on Study Days 1, 2 and 3 will not be attempted.

Incidence rates would be assessed across

- i) the entire study (the outcome taking the value of the worst case observed) and
- ii) on an individual visit basis (Note: Screening and Day 1 data would be combined and labelled as Day 1; the worst case outcome used in any combination)

The following rates would be assessed

- Incidence rates of ARDS diagnosis
- Incidence rates of PCD or ACP (any right ventricular dysfunction; regardless of PCD or ACP severity level)
- Incidence rates of PCD (Moderate PCD (not severe enough to qualify as ACP))
- Incidence rates of Non-severe ACP
- Incidence rates Severe ACP

Additionally, the worst case PCD/ACP diagnosis across the study would be combined with the ARDS diagnosis to form the following categories

- ARDS and No PCD or ACP
- ARDS and PCD
- ARDS and Non-Severe ACP
- ARDS and Severe ACP

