7.2.2. Summary Measure

For the Ang(1-7) and Ang(1-5) endpoints described above:

- The posterior predictive probability of RV dysfunction for pre-determined “pre-dose” Ang II and Ang(1-7) values (or Ang(1-5)),

- The posterior predictive probability of RV dysfunction for pre-determined “post-dose” Ang II and Ang(1-7) values (or Ang(1-5)), and
- The difference between the two (Note: Although the difference will still be computed as Pre-Post for Ang(1-7) and Ang(1-5) negative values would be a favourable outcome).

For the incidence rate variables

- The At Risk population would be used to filter the individuals going into the subsequent analysis dataset
- For rates relating to an individual visit
 - The big N value would not represent distinct participants but instead represents the maximum number of visits in the analysis dataset (derived by counting the number of subject visits where any ARDS or PCD/ACP assessment was made (expecting three visits per subject – but may reduce if subjects withdraw/die before day 3))
 - the little n value would represent the number of completed visits for that item
 - Freq. represents the number of positive occurrences (Subjects with a Yes response)
 - Rate (%) = $100 * \text{Freq.} / \text{n}$ [little n]
 - The 95% CI for the rate (%) should be derived using Wilson Score interval with continuity correction methodology
- For rates relating to the entire study
 - The big N value represents the number of participants for whom an ARDS or PCD/ACP assessment was made at any time in the study
 - Freq. represents the number of positive occurrences (Subjects with a Yes response)
 - Rate (%) = $100 * \text{Freq.} / \text{N}$ [big N]
 - The 95% CI for the rate (%) should be derived using Wilson Score interval with continuity correction methodology

Any modifications to the above would be described in the CSR.

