7.2.5.3. Analysis of disease incidence within the mechanically ventilated population

The incidence of ACP and PCD in the population will be presented as summary tables, by study day, and overall (i.e. diagnosis at any time during the three-day study period).

Descriptive statistics (N (population), #Occurrences (Freq.), number at risk (n), Incidence Rate and 95% CI for Rate (methodology for 95% CI: Wilson Score interval with continuity correction))

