10.10.6. Pharmacodynamic and Biomarker Tables

Pharmacodynamic and Biomarker: Tables					
No.	Population	IDSL / Example Shell	Title	Programming Notes	Deliverable [Priority]
Echocardiography					
3.1.	Evaluable	PD_T1 (ECHO)	Summary of Echocardiogram Measurements by Timepoint	Two separate statistics tables: 1) for continuous, 2) for qualitative echo measurements.	SAC 1
3.2.	Evaluable	SM_T1 (ECHO)	Within- and Between-Subject Variability of Continuous Echocardiogram Measurements		SAC 1
RAS Biomarkers					
3.3.	Evaluable	PD_T2 (RAS)	Summary of RAS Biomarker Measurements by Timepoint	Present results for levels and log transformed in two separate tables.	SAC 1
3.4.	Evaluable	SM_T1 (RAS)	Within- and Between-Subject Variability of RAS Biomarker Measurements		SAC 1

Participant Status and Other Clinical Assessments: Tables					
No.	Population	IDSL / Example Shell	Title	Programming Notes	Deliverable [Priority]
Disease Diagnosis Status					
4.1.	At risk	OCA_T1 (DISEASE_INCIDENCE)	Summary of ARDS, PCD and ACP Incidence Rates by Timepoint and Study	Create two tables: 1) summarizing of number of the cases, where patient may contribute multiple times and 2) with overall incidence rates including the joint categories. Note: Shell does not contain all items to be displayed	SAC 1

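### Whole-study ARDS, PCD and ACP rates share one denominator, so a participant never assessed for a condition is counted as free of it

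*SAP*

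**What the plan says.** SAP 7.2.2 has two rules for incidence rates, both applied to the At Risk population.

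- **Whole-study rates.** One line defines the denominator: "The big N value represents the number of participants for whom an ARDS or PCD/ACP assessment was made at any time in the study". The rate is 100 × Freq./N, and Freq. counts participants with a positive response. No item-specific n is defined.
- **Individual visit.** A pooled N is again defined, but the rate is 100 × Freq./n, where "the little n value would represent the number of completed visits for that item".

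SAP section 4 admits a participant to At Risk either with PASP and RV size ratio on all three days or, under its second criterion, with a "databased ACP/PCD and/or ARDS assessment during the study period". One type of assessment is enough.

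SAP 7.2.1 adds that "Screening and Day 1 data would be combined and labelled as Day 1; the worst case outcome used in any combination", and that "the worst case PCD/ACP diagnosis across the study would be combined with the ARDS diagnosis to form the following categories": ARDS with no PCD or ACP, with PCD, with non-severe ACP, and with severe ACP. SAP 7.2.5.3, which covers the summaries by study day and overall, lists "number at risk (n), Incidence Rate and 95% CI for Rate" among the statistics. The notes to Table 4.1 (SAP 10.10.6) ask for a second table "with overall incidence rates including the joint categories".

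**The concern.** Under the whole-study rule, a participant with no assessment of an item adds nothing to that item's numerator and one to its denominator. Missing status is in effect read as absence of disease. The by-visit rule shows that the authors foresaw item-level missingness and allowed for it there. The whole-study rule does not, although SAP 7.2.5.3 calls for a number at risk in the overall table too.

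The incidence of ACP and PCD is a secondary objective. Protocol 10.1 uses ACP incidence to support the sample size, and SAP section 1 keeps the secondary outputs after early termination. If anyone in N was not assessed for an item, three things follow:

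- that item's rate is too low as an estimate among those assessed;
- its interval is computed on too many participants;
- an ARDS-positive participant with no PCD/ACP assessment falls in none of the four joint categories but stays in their denominator.

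**Working it through.** **1. The plan's own figure.** Protocol 10.1 states a precision of ±5 percentage points (95% Wald half-width) for an ACP incidence of 10% with 150 participants:

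1.96 × √(0.10 × 0.90 / 150) = 0.0480, or 4.8 points.

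This rounds to the stated value. It treats all 150 as assessed for ACP.

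**2. Effect of the shared denominator.** Let n be the number assessed for the item and m = (N − n)/N. Then

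Freq./N = (Freq./n) × (n/N) = rate among those assessed × (1 − m).

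The error can only be downward. For a 10% rate among those assessed, with m assumed:

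| m | Reported rate |
|---|---|
| 0% | 10.0% |
| 5% | 9.5% |
| 10% | 9.0% |
| 20% | 8.0% |

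**3. Intervals by the SAP's method** (Wilson score with continuity correction). With p = Freq./n and z = 1.96:

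- lower = [2np + z² − 1 − z√(z² − 2 − 1/n + 4p(n(1 − p) + 1))] / [2(n + z²)]
- upper = [2np + z² + 1 + z√(z² + 2 − 1/n + 4p(n(1 − p) − 1))] / [2(n + z²)]

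The documents do not give the final N. Two sizes are used for illustration: 50 (the planned second interim) and 150 (the planned maximum). Recorded ACP cases are assumed to be 10% of N. The first row for each N is what the shared rule reports however many participants are unassessed.

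| N | Not assessed for PCD/ACP (assumed) | Freq./n | Rate | 95% CI |
|---|---|---|---|---|
| 50 | 0 | 5/50 | 10.0% | 3.7–22.6 |
| 50 | 1 | 5/49 | 10.2% | 3.8–23.0 |
| 50 | 5 | 5/45 | 11.1% | 4.2–24.8 |
| 50 | 10 | 5/40 | 12.5% | 4.7–27.6 |
| 150 | 0 | 15/150 | 10.0% | 5.9–16.2 |
| 150 | 8 | 15/142 | 10.6% | 6.2–17.1 |
| 150 | 15 | 15/135 | 11.1% | 6.6–18.0 |
| 150 | 30 | 15/120 | 12.5% | 7.4–20.1 |

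**4. Joint categories.** Assume 20 of 50 are ARDS-positive and 4 of those have no PCD/ACP assessment. The ARDS rate is 20/50 = 40.0%. The four joint categories sum to (20 − 4)/50 = 32.0%, an unexplained gap of 8.0 points.

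**5. Can a participant have only one type of assessment?** The schedule of activities (Protocol section 2) collects ARDS status from screening, but PCD/ACP only from the Day 1 to 3 echocardiograms. Footnote 1 there lets screening count as part of Day 1, and SAP 7.2.1 merges the two. Protocol 5.3 treats a participant with no echocardiogram as withdrawn, but the At Risk definition excludes only withdrawn consent. SAP 7.1.4 also foresees unusable echo views. The routes are open, and the documents do not say how many participants take them.

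**6. Programming source.** The SAP does not name the dataset behind Table 4.1. If it is ALLCVTS (SAP 10.6.10), rows need an evaluable PASP or RV size ratio, so participants with no echocardiogram drop out. Its ARDSX and PCDACPX flags, however, default to N when no diagnosis is recorded, so unassessed participants who remain are still non-cases.

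**The case against.** The strongest reply is that the problem may never arise.

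- **No echocardiogram.** Protocol 5.1 defines Day 1 by the first echocardiogram, SAP 10.6.1 counts study days from it, and the Protocol synopsis gives a 3-day study period. A screening-only ARDS record could thus be said to fall outside the study period and not qualify for At Risk.
- **Poor views.** SAP 7.1.4 concerns single timepoints in the primary model. Transoesophageal imaging is used when transthoracic windows are inadequate (Protocol 9.2.1), acceleration time replaces a missing pressure gradient (9.5.3), and one assessment in three days is enough for the any-time rate.
- **ARDS missing.** ARDS status is scheduled at screening and with every echocardiogram, so the reverse case is less likely still.
- **Size.** One unassessed participant in 50 moves 10.0% to 10.2%, inside an interval of 3.7 to 22.6. The rates are descriptive, and no decision rule uses them.
- **Traceability.** The by-visit table carries an item-specific n, and Listing 15 gives diagnosis status for the At Risk population.
- **Joint categories.** An item-specific n does not make them add up: in the example above, ARDS stays at 20/50 = 40.0% while the joint categories give 16/46 = 34.8%.

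Most of this stands as a limit on size. The routes are narrow, but the schedule places screening under the study period and footnote 1 lets it count as Day 1, so they are not closed. None of it changes the rule as written, and a reader of the overall table could not see the effect. The last point is correct: what the change provides is a visible n that explains the gap, not categories that sum to the ARDS rate.

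The or in the definition might also be read as whichever item applies. The single N, the parallel by-visit wording and the absence of a whole-study n count against that reading, and it would leave the joint categories with no denominator.

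**Conclusion.** The concern holds. The whole-study rule in SAP 7.2.2 counts participants never assessed for a condition as not having it, contrary to the by-visit rule beside it. The direction (downward) and the factor (1 − m) follow from the stated formula. The size cannot be found from the documents, because m, the final N and the case counts are not given and the values used here are assumptions. If every participant in N has both assessments there is no effect. For small m the shift is well inside the confidence interval. This is therefore a rule to correct before Table 4.1 is produced, not evidence that the reported rates will be materially wrong.

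**What to change.** In SAP 7.2.2, define a whole-study n for each item:

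- PCD and ACP rates: participants with at least one PCD/ACP assessment;
- ARDS rate: participants with at least one ARDS assessment;
- joint categories: participants with both.

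Compute the rate as 100 × Freq./n and the Wilson interval on n. Show N and n in the overall table, which also gives meaning to the number at risk in 7.2.5.3. If ALLCVTS feeds Table 4.1, leave the ARDS and PCD/ACP flags missing when no assessment exists.

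Add a footnote that a participant negative on Day 1 and not reassessed still counts as a non-case. At Risk accepts fewer than three days of assessments, and echocardiography after extubation depends on standard of care (Protocol 5.3), so this change does not cure partial follow-up.

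As an optional wording point, Protocol 10.3.1 separates incidence during the study from prevalence on entry. The table could label the Day 1 row as prevalence on entry and note that the any-time rate includes cases already present then.

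The cost is a few lines of SAP text, one column and one footnote, with no new data. Denominators may be slightly smaller and intervals slightly wider. Nothing changes if no one is unassessed.

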7.2.3. Population of Interest

The secondary pharmacodynamic analyses will be based on the Evaluable population, unless otherwise specified.

All analyses involving incidence rate endpoints will be based on the At Risk population unless otherwise specified.

7.2.4. Strategy for Intercurrent (Post-Randomization) Events

Since there is no investigational product in the study simplistic approaches will be taken to deal with intercurrent events. Any data driven alternative strategies implemented would be described in the CSR.

7.2.5. Statistical Analyses / Methods

The secondary statistical analyses are divided into three subcategories, with the first being variations on the primary analysis: analyses following the same form as the primary analysis but using a different RAS peptide measurement in place of Ang II.

The second subcategory models the joint association of Ang II and Ang(1-7) on RV function (Note: if the observed data ranges do not permit parameter estimation/model convergence of the proposed model then simpler alternative models may not be attempted; but if they are any methodology would be described in the CSR).

The third subcategory of the secondary analyses is an estimate of disease incidence within the mechanically ventilated population.

Details of the planned displays are provided in [Appendix 10](#): List of Data Displays and will be based on GSK data standards and statistical principles.

Unless otherwise specified, endpoints / variables defined in Section [7.2.1](#) will be summarised using descriptive statistics, graphically presented (where appropriate) and listed.

7.2.5.1. Supportive Models to the Primary analysis, using other RAS peptides in place of Ang II

Supportive models to the primary analysis will be conducted following the same methodology as the primary analysis models (see Section [7.1](#)) but with changes as described below.

The first supportive model will include Ang(1-7) as a time-point-level covariate instead of Ang II, and the corresponding reference value from Section [7.1.5](#).

Note: An optional supportive model would include Ang(1-5) as a time-point-level covariate instead of Ang II, and the corresponding reference value from Section [7.1.5](#). This model may be attempted if the Ang II and Ang(1-7) modelling does not produce a clear/consistent outcome and/or the observed level of correlation between Ang(1-5) and Ang(1-7) data is deemed likely to result in a different conclusion (*a priori* expectation Ang(1-7) and Ang(1-5) data will be highly correlated, and so any modelling would be expected to produce similar conclusions and duplication would not add value).

7.2.5.2. Combined model of the joint association of Ang II and Ang (1-7) with RV function

Endpoint / Variables

 PASP and RV Size Ratio on Day 1, Day 2 and Day 3 where available Time matched concentration of Ang II (Denoted as A in model specification) Time matched concentration of Ang (1-7) (Denoted as B in model specification)
Model Specification
The relationship between Ang II and Ang(1-7) (as joint explanatory variables) and the

joint bivariate distribution of PASP and RV size ratio (the outcome variables) will be analysed using a Bayesian multivariate non-linear regression model.

For simplicity, the repeated measures aspect of the data structure is not being modelled by first intent and Hill coefficients are assumed to be 1. If data permit, a similar strategy to the primary analysis that accounts for repeated measures may be attempted (e.g. Kronecker product with an AR(1) structure for Tigma), but only the model used for final inference would be reported. If data do not permit the planned model to be fitted no further modelling is proposed. However, if alternative model(s) are attempted and successful, they would be described in the CSR).

The multivariate normal model is specified as follows (for maximum flexibility time has been left in the parameter definitions) :

$$\begin{pmatrix} y_{it1} \\ y_{it2} \end{pmatrix} \sim MVNormal \left(\begin{pmatrix} \mu_{it1} \\ \mu_{it2} \end{pmatrix}, \Sigma \right)$$

where y_{itj} represents the observed value for the i th participant, the t th time-point and the j th outcome (i.e. $j = 1$ representing PASP and $j = 2$ representing RV size ratio), μ_{itj} represents the expected value for the i th participant, t th time-point ($t = 1, 2, 3$) and the j th outcome ($j=1$ and $j=2$ as above), and Σ represents a variance-covariance (vcov) matrix for the two outcome variables.

The expected values, μ_{itj} , are modelled as follows:

$$\mu_{itj} = \frac{Basal_j + Max_{Bj} \frac{[B]}{EC_{50jB}|A=0} + Max_{Aj} \frac{[A]}{EC_{50jA}|B=0} + Max_{ABj} \frac{[A][B]}{EC_{50jA}|B=0 EC_{50jB}|A \rightarrow \infty}}{1 + \frac{[B]}{EC_{50jB}|A=0} + \frac{[A]}{EC_{50jA}|B=0} + \frac{[A][B]}{EC_{50jA}|B=0 EC_{50jB}|A \rightarrow \infty}}$$

Where,

$Basal_j$ is the response in the absence of A and B for the j th outcome

Max_{Aj} is the response to saturating concentrations of A in the absence of B for the j th outcome

Max_{Bj} is the response to saturating concentrations of B in the absence of A for the j th outcome

Max_{ABj} is the response in the presence of saturating concentrations of both ligands for the j th outcome

$EC_{50jA}|B=0$ is the EC₅₀ of A in the absence of B for the j th outcome

$EC_{50jB}|A=0$ is the EC₅₀ of B in the absence of A for the j th outcome

$EC_{50jB}|A \rightarrow \infty$ is the EC₅₀ of B in the presence of saturating concentrations of A for the j th outcome

[A] is time matched concentration of AngII (to aid review $[A_{it}]$ notation not used)

[B] is time matched concentration of Ang(1-7) (to aid review $[B_{it}]$ notation not used)

Also note that $EC_{50jA|B=0} \times EC_{50jB|A \rightarrow \infty} = EC_{50jB|A=0} \times EC_{50jA|B \rightarrow \infty}$, so the equation is symmetrical in A & B.

The vcov structure for $\Sigma_{(6 \times 6)}$ is constructed using the same approach as the primary analysis model but with an Identity matrix used for Tigma by first intent

$$\Sigma = \text{Sigma} \otimes \text{Tigma} =$$

$$\begin{pmatrix} \sigma_{y_1}^2 & \sigma_{y_1 y_2} \\ \sigma_{y_1 y_2} & \sigma_{y_2}^2 \end{pmatrix} \otimes \begin{pmatrix} 1 & 0 & 0 \\ 0 & 1 & 0 \\ 0 & 0 & 1 \end{pmatrix} \text{ and}$$

$$Var \begin{pmatrix} y_{t11} \\ y_{t21} \\ y_{t31} \\ y_{t12} \\ y_{t22} \\ y_{t32} \end{pmatrix} = \begin{pmatrix} \sigma_{y_1}^2 & 0 & 0 \\ 0 & \sigma_{y_1}^2 & 0 \\ 0 & 0 & \sigma_{y_1}^2 \\ \sigma_{y_1 y_2}^2 & 0 & 0 \\ 0 & \sigma_{y_1 y_2}^2 & 0 \\ 0 & 0 & \sigma_{y_2}^2 \end{pmatrix} \begin{pmatrix} \sigma_{y_1 y_2}^2 & 0 & 0 \\ 0 & \sigma_{y_1 y_2}^2 & 0 \\ 0 & 0 & \sigma_{y_1 y_2}^2 \end{pmatrix} \begin{pmatrix} \sigma_{y_2}^2 & 0 & 0 \\ 0 & \sigma_{y_2}^2 & 0 \\ 0 & 0 & \sigma_{y_2}^2 \end{pmatrix}$$

Uninformative prior distributions are assigned for the parameters as follows:

- Model parameters Basal_j, Max_{Aj}, Max_{Bj}, Max_{ABj}, EC_{50jA|B=0}, EC_{50jB|A=0} and EC_{50jB|A → ∞} (for j=1 (PASP) and 2 (RV Size ratio)) will each be assigned a prior of Normal(Mean=0, Var=1^E6). Note: By first intent these are all independent prior statements and correlation structures between related parameters would be expected to be observed in the observed posterior covariances of the model parameters (see Sensitivity analyses sections for alternative prior structures if model convergence issues are encountered).
- Σ , defined as the inverse of Sigma , is assigned an uninformative Wishart prior distribution: $\Sigma \sim \text{Wishart}(R, df)$ where: $R = \begin{pmatrix} 0.01 & 0 \\ 0 & 0.01 \end{pmatrix}$ and $df = 3$.
-

Model Checking & Diagnostics

- As per Primary analysis

Model Results Presentation

- Once the model parameters have been estimated analogous predictions of the Posterior Probability of RV dysfunction (and differences between pre and post dose AngII levels) would be obtained as per Primary analysis. However, twice the number of items would be produced because there would be a need to condition on the two “pre and post dose” values for Ang(1-7) for each set of Ang II values.

Subgroup Analyses

- Not planned

Sensitivity and Supportive Analyses

- If model convergence issues are encountered the prior structure may be modified to group related sets of parameters together using a MVN (multivariate normal distribution). Two MVN priors distributions may be set up (one for each j) using parameters Basal_j , Max_{Aj} , Max_{Bj} , Max_{ABj} , $\text{EC}_{50jA|B=0}$, $\text{EC}_{50jB|A=0}$ and $\text{EC}_{50jB|A \rightarrow \infty}$. The MVN mean would be a vector of zeros and the prior for the vcov matrix of the model parameters would be an inverse-wishart with $R=Identity(7 \times 7)$ and $df=7$.
- An AR(1) structure may be attempted for the Σ vcov matrix and would use an uninformative uniform prior distribution over $-1, 1$ interval for parameter ρ

